On this day, prior to socket fitting activities, the arterial blood flow will be measured on the index stump if not already completed per standard of care within the previous 12 months prior to enrollment for data analysis. Those with an TcOM < 30 mmHG be excluded and no further study activities will be completed. These subjects will be recorded as a screen fail and will not be enrolled.

Others will move forward with socket fitting activities.

- A. **Study Visit #1 - Socket Fitting visits (Week 0 - 4, +/- 2 weeks) – Note: this visit may consist of three (minimum) visits plus socket adjustment visits (as needed by the subject) on separate days (up to 4 weeks)**
 - i) limb shape capture, measurements or tracing
 - ii) diagnostic static fitting and diagnostic dynamic fitting
 - iii) delivery of definitive “research” socket

Once delivery of the definitive research socket has been completed, the subject will be allowed to return for no greater than 4 adjustments (within 0-2 weeks from baseline) to obtain a comfortable fit in order to complete this study. If subject requires more than 4 adjustment visits, the participation from the study will end.

Once the subject is comfortable with the fitting, the date will be noted by the study team as **“research socket use start date”**. From this date, the subject will begin wearing the test socket for next 16 weeks.

- B. **Study Visit #2A - Baseline visit for residual limb health (Week 4, +/- 2 weeks)** Enrollment, after delivery of the definitive research socket and completion of the socket fitting visits, the following research activities will take place to obtain baseline measurements:

- Subjects will be asked to walk on a treadmill for 10 mins. The residual and sound (intact) limb health measurements will be taken before and after the activity period with the exception of conducting post-activity ultrasound and digital imaging. The purpose of acquiring ultrasound and digital imaging is to determine changes in skin structure on a long-term basis; thus, these measurements will only be collected during pre-activity procedures to observe changes in a resting state. The following health measurements will take place:
 - Surface Electrical Capacitance
 - TEWL measurement
 - Hyperspectral Imaging
 - Ultrasound (pre-activity only)
 - Perfusion/ Blood flow
 - Digital Image (pre-activity only)

B.i. Study Visit #2B - Baseline visit for gait assessment (Week 4, +/- 2 weeks)**

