***Note* Study Visit #2A and #2B can be combined and performed in a single study visit upon the discretion of the subject.**

Subjects will begin in their current standard of care prosthesis (the prosthesis worn at time of study enrollment), wherein the following research activities will take place in the following order:

- Subjective questionnaires [Veterans RAND 36-Item Health Survey (VR
- 36, PEQ, Socket Comfort Scores (SCS), and National Institute of Health (NIH) Patient-Reported
- Outcomes Measurement Information System (PROMIS)
- Functional evaluation [Comprehensive High-level Activity Mobility Predictor (CHAMP)]
- Biomechanical evaluation of gait during 6min walking test
 - a. Positioning markers will be placed on the subject while performing the walking assessment to track and describe the movement of the body in three dimensions.
- Repeat SCS outcome

**** applicable to any new enrollments and/or any already enrolled subject completed their limb health part (16 weeks in test sockets followed by 4 weeks in SoC socket as wash off period)**

Following completion of these activities in study visit 2A & B, the subjects will be fitted with the adaptive vacuum suspension by a certified prosthetist that they will wear subsequently wear the device for 16 weeks

The study team will follow up subjects with a weekly phone call to determine the compliance for the use of research socket.

C. **Study Visit #3A – Final Visit (Week 16, +/-2 weeks).** After 16 weeks of wearing the “research” socket the following research activities will take place in the following order:

- Subjects will be asked to walk on a treadmill for 10 mins. The following residual and sound limb health measurements will be taken before and after the activity period with the exception of conducting post-activity ultrasound and digital imaging, is as follows
 - Surface Electrical Capacitance
 - TEWL measurement
 - Hyperspectral Imaging
 - Ultrasound (pre-activity only)
 - Perfusion/ Blood flow
 - Digital Image (pre-activity only)

C.i **Study Visit #3B**— the visit will take place either the same day of Visit 3A or another day within the Week 16, +/-2 weeks based on subject convenience, to repeat research activities previously performed in study visit # 2A

- Subjective questionnaires [Veterans RAND 36-Item Health Survey (VR 36, PEQ, Socket Comfort Scores (SCS), and National Institute of Health (NIH) Patient-Reported Outcomes Measurement Information System (PROMIS)]

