All subjects will be compensated \$100 for each of the completed visits. Aim 1 subjects will be compensated \$100 for the completed study visit 1. Aim 2 subjects will have 4 total visits and will be eligible for a maximum of \$400 for completion of all study visits. Aim 3 subjects will have 3 total visits and will be eligible for a maximum of \$450 for the completion of all visits per following schedule: Visit #1 (\$50), Visit #2A & B (\$150, for completing all socket fitting activities

& baseline) and Visit #3A&B (\$250). Subjects will not be paid if any of study visits are not completed.

XV. Statistical Analysis:

Patient demographics and clinical characteristics will be described using frequencies and percentages for categorical data and median and the interquartile range (IQR) for continuous data. In Aim 1, random-effects linear regression will be used to assess the relationship between wave amplitude and distal movement (or lateral shift) controlling for vacuum pressure. Patient ID will be the random-term in the model. In Aim 2, random-effects linear regression will also be used to compare percent change in limb perfusion across adaptive EVS and suction at 12 weeks controlling vacuum pressure and controlling for the baseline EVS and suction values. In Aim 3, a random-effects linear regression model will be used to establish the relationship in amputee performance (as measured by the CHAMP tasks) and residual limb health across EVS and suction and across EVS and pin-locking/lanyard in a cross-over design. The model includes terms for group (EVS vs. suction or EVS vs. pin-locking/lanyard), sequence (EVS to suction vs. suction to EVS or EVS to pin-locking/lanyard vs. pin-locking/lanyard to EVS), and visit (second vs. first). All statistical models will account for the effect of age, diabetes status and smoking history by including them as the covariates in the models. As per need, subjects may be stratified based upon diabetes status and arterial blood flow status. The *p*-values produced in the study will be adjusted using the Holms procedure to control the overall type I error at 0.05 due to the multiple comparisons. All analyses will be run using Stata 13.1, Stata Corporation, College Station, Texas.

XVI. References:

1. Lake, C. The evolution of upper limb prosthetic socket design. *Journal of Prosthetics and Orthotics* 20, 85 (2008).

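### The Aim 3 limb-health model is a two-order cross-over, but the IU schedule has one order, so time and device cannot be separated and the sound-limb readings that could help are unused.

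*Combined protocol and SAP*

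**What the plan says.** **Measurements.** Section VIII.B (Study Visit #2A, baseline limb health) says: "The residual and sound (intact) limb health measurements will be taken before and after the activity period". Section VIII.C (Study Visit #3A, final) repeats this: "The following residual and sound limb health measurements will be taken before and after the activity period". At both visits, ultrasound and digital images are taken before activity only.

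**Order of devices.** Section VIII.A sets a start date once the fit is comfortable: "From this date, the subject will begin wearing the test socket for next 16 weeks". After visits 2A and 2B, section VIII adds that "the subjects will be fitted with the adaptive vacuum suspension by a certified prosthetist". The final readings follow 16 weeks of wear. No subject is scheduled to take the devices in the reverse order, and no limb-health visit follows a return to standard of care. The four-week wash-off note is attached to the gait visit (2B), not to limb health.

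**Analysis.** Section XV plans a random-effects model for "residual limb health across EVS and suction and across EVS and pin-locking/lanyard in a cross-over design". Besides group, its terms are "sequence (EVS to suction vs. suction to EVS or EVS to pin-locking/lanyard vs. pin-locking/lanyard to EVS), and visit (second vs. first"). On covariates: "All statistical models will account for the effect of age, diabetes status and smoking history by including them as the covariates in the models". The sound limb appears neither as an outcome nor as a contrast or covariate. There is no term for calendar date or instrument.

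**The concern.** In a two-order cross-over, the visit term separates a shift over time from the device effect, because some subjects meet the new device first and others second. With one order that separation is lost. Skin hydration, TEWL, perfusion and oxygenation could move between the two visits with room conditions, instrument calibration or general health. A movement of that kind common to all subjects would be reported as benefit or harm of the vacuum system.

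The sound limb is read at the same two visits with the same listed measurements. It is the only information in the IU schedule on what would have happened to skin readings over that interval without a change of socket. If its role is left unstated, a choice between contrasts could also be made after the data are seen.

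**Working it through.** The plan gives no power, effect size or SD for Aim 3, so there is no figure of its own to reproduce.

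**Inputs from the documents**
- Model terms: group, sequence and visit (section XV).
- One device order at IU (section VIII.A to C).
- n=30 at IU. The planned limb-health total is n=60, from IU plus Willow Wood (section VIII, rationale for the amendment).
- Overall type I error 0.05 with Holm adjustment (section XV).

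**Assumptions**
- Two-sided tests.
- Common shift d between visits of 0.2 or 0.3 SD of the within-person change, with no device effect.
- 6 tests in the Holm family.
- Correlation r between residual-limb and sound-limb change of 0 to 0.7, with equal SDs.

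**Step 1: can the model be fitted?** Take the columns as intercept, group, sequence, visit. With one order, each subject gives (1, 0, 0, 0) at baseline and (1, 1, 0, 1) at the final visit. Sequence is constant, and visit is identical to group. The rank is 2 of 4. With two orders (30 + 30) the rank is 4 of 4. Age, diabetes status and smoking history describe the subject rather than the visit, so as main effects they do not separate visit from group.

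**Step 2: where does a shift go?** For a shift of 0.3 SD and a device effect of 0:
- Two orders: group coefficient 0.00, visit coefficient 0.30.
- One order, with the redundant term dropped: group coefficient 0.30.

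**Step 3: false-positive rate for residual-only change.** The test is a one-sample t test of the change, with noncentrality d√n on n − 1 degrees of freedom. For d = 0.2 this is 0.2 × √30 = 1.10 and 0.2 × √60 = 1.55. The first Holm step with 6 tests uses 0.05/6 = 0.0083.

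| Shift | n | Level 0.05 | Level 0.0083 |
|---|---|---|---|
| 0.2 SD | 30 | 19% | 5% |
| 0.2 SD | 60 | 33% | 13% |
| 0.3 SD | 30 | 36% | 14% |
| 0.3 SD | 60 | 63% | 35% |

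These are per-test rates, not family-wise rates. With no shift they would be 5% and 0.83%.

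**Step 4: residual-minus-sound change.** If both limbs shift equally, d − d = 0 and the rejection rate returns to about 5%. The standard error relative to residual-only change is √(2(1 − r)):
- r = 0: 1.41
- r = 0.3: 1.18
- r = 0.5: 1.00
- r = 0.7: 0.77

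**The case against.** **The plan has its own control for drift.** Section XV includes a visit term, and in the cross-over it describes, that term would absorb a shared shift (step 2). This stands. A reader might infer that the written model is blind to time, but it is not. The term fails only because the section VIII schedule has one order, and that mismatch is the root fault.

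**Drift is not shown.** Nothing in the documents reports drift of any size. Seasonal change over a fixed interval tends to average out if entry is spread over the year, and biases the mean only if entry is clustered. This also stands.

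**The endpoint is undefined.** Section XV does not say whether residual limb health means a resting level or the change from before to after activity. If it is the within-visit change, a constant instrument offset already cancels. Resting levels, and the ultrasound and images taken before activity only, remain exposed.

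**The sound limb is an imperfect control.** It is not in a socket, so equal shifts are doubtful. Suppose the residual limb shifts 0.1 SD, the sound limb 0.3 SD, and r = 0.5. Residual-only change then rejects 8% (n=30) or 12% (n=60) of the time at 0.05. The contrast shifts by 0.1 − 0.3 = −0.2 SD with a standard-error ratio of 1.00, so it rejects 19% or 33%, which is worse. For this reason the contrast should stand beside the residual-only change and not replace it.

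**The n=60 figures.** Section V says OWW works under a separate IRB protocol. Whether its visits match IU's cannot be seen here.

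**Conclusion.** The point holds as a mismatch between model and schedule, with an unused partial remedy. At IU the planned limb-health model cannot distinguish device from time, and the plan gives no role to the one concurrent comparison it collects.

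The rank result needs only the schedule and the listed terms. The rejection rates rest on the assumed shift, and the Holm figures on an assumed family of 6. They show the scale of the exposure and do not predict error in this trial.

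Two stronger readings are tempting. One is that season or instrument drift will bias the result, but the documents give no evidence of such drift. The other is that residual-minus-sound change is the device effect. It is not: the contrast removes only drift shared equally by both limbs. It leaves residual-limb maturation in place (section III admits subjects from 3 months after amputation), and it may be biased if the device changes loading of the sound limb.

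The baseline itself is also unclear. Section VIII.B places visit 2A after delivery of the research socket, while the text after visit 2B places fitting of the vacuum suspension after both visits. If the baseline reading belongs to the research socket, group does not vary between the two visits and the schedule gives no comparison of devices for limb health.

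**What to change.** 1. Describe the IU limb-health comparison as before/after, and remove the sequence and visit terms that its schedule cannot support.
2. Pre-specify an added model with both limbs, subject as random effect, and terms for limb, visit and limb × visit. Report residual-minus-sound change (limb × visit) alongside residual-only change.
3. Require the two to agree before a change is attributed to the device, and define agreement in advance. State that neither estimate removes residual-limb maturation.
4. Define the limb-health endpoint for each measure: resting level or change with activity.
5. Reconcile the passages in section VIII on which device is worn at the baseline limb-health reading.
6. State whether OWW follows the IU schedule.

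**Cost.** The readings are already planned, so this is an edit to section XV plus the clarifications in section VIII. The price is precision when the between-limb correlation is below 0.5, with a standard error 41% wider at r = 0 and 18% wider at r = 0.3. For an assumed true effect of 0.5 SD at n=30 and unadjusted 0.05, simulated power is about 0.75 for residual-only change, and 0.60, 0.75 and 0.92 for the contrast at r = 0.3, 0.5 and 0.7. Requiring agreement makes a positive conclusion harder to reach than either analysis alone.

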***Note* Study Visit #2A and #2B can be combined and performed in a single study visit upon the discretion of the subject.**

Subjects will begin in their current standard of care prosthesis (the prosthesis worn at time of study enrollment), wherein the following research activities will take place in the following order:

- Subjective questionnaires [Veterans RAND 36-Item Health Survey (VR
- 36, PEQ, Socket Comfort Scores (SCS), and National Institute of Health (NIH) Patient-Reported
- Outcomes Measurement Information System (PROMIS)
- Functional evaluation [Comprehensive High-level Activity Mobility Predictor (CHAMP)]
- Biomechanical evaluation of gait during 6min walking test
 - a. Positioning markers will be placed on the subject while performing the walking assessment to track and describe the movement of the body in three dimensions.
- Repeat SCS outcome

**** applicable to any new enrollments and/or any already enrolled subject completed their limb health part (16 weeks in test sockets followed by 4 weeks in SoC socket as wash off period)**

Following completion of these activities in study visit 2A & B, the subjects will be fitted with the adaptive vacuum suspension by a certified prosthetist that they will wear subsequently wear the device for 16 weeks

The study team will follow up subjects with a weekly phone call to determine the compliance for the use of research socket.

C. **Study Visit #3A – Final Visit (Week 16, +/-2 weeks).** After 16 weeks of wearing the “research” socket the following research activities will take place in the following order:

- Subjects will be asked to walk on a treadmill for 10 mins. The following residual and sound limb health measurements will be taken before and after the activity period with the exception of conducting post-activity ultrasound and digital imaging, is as follows
 - Surface Electrical Capacitance
 - TEWL measurement
 - Hyperspectral Imaging
 - Ultrasound (pre-activity only)
 - Perfusion/ Blood flow
 - Digital Image (pre-activity only)

C.i **Study Visit #3B**— the visit will take place either the same day of Visit 3A or another day within the Week 16, +/-2 weeks based on subject convenience, to repeat research activities previously performed in study visit # 2A

- Subjective questionnaires [Veterans RAND 36-Item Health Survey (VR 36, PEQ, Socket Comfort Scores (SCS), and National Institute of Health (NIH) Patient-Reported Outcomes Measurement Information System (PROMIS)]
- Functional evaluation [Comprehensive High-level Activity Mobility Predictor (CHAMP)]
- Biomechanical evaluation of gait during 6min walking test
- Repeat SCS outcome

- The subjects will be given a choice to keep the research socket or return to using their original prosthesis as normal. The study prosthetist will be available to review and adjust the fit of their standard of care prosthesis at this time. Note; Due to physical change and limb volume fluctuation over the study period, it is possible that at the end of the study the standard of care prosthesis will not fit your residual limb as it does at the beginning of the study. At the completion of the study it is recommended that the subject follow up with their primary care prosthetist for socket evaluation and fitting.
- Any research-related tests or activities are performed at the expense of the research study and will not be billed to you or your insurance.
- Any non-research related activities, tests, or necessary medical treatment will be provided to you and billed as part of your medical expenses. Costs not covered by your health care insurer will be your responsibility. Also, it is your responsibility to determine the extent of your health care coverage.

Walter Reed National Military Medical Center (WRNMMC) will recruit and enroll 60 subjects with a pin-locking prosthesis and has separate IRB approval to conduct the study. The study visits will be per their approved IRB protocol (see attached).

IX. Study Procedures:

There may be risks that are not known about at this time. Side effects, risks, and discomforts may result from study participation.

- A. Demographic, medical, and subjective questionnaires: Subjects will be queried on self-reported measures of user comfort and performance. Briefly, four subjective measures will be completed: VR-36, PEQ, SCS, and measures from the NIH PROMIS. The VR-36 was developed from the original RAND version of the Medical Outcomes Study 36-Item Health Survey as a short form functional assessment for veterans. The PEQ is composed of 9 validated scales to measure various aspects of a prosthesis and the users feelings about it. The scales include: Ambulation, Appearance, Frustration, Perceived Response, Residual Limb Health, Social Burden, Sounds, Utility, and Well Being. The SCS is based on a 0-10 numerical scale that assesses comfort rather than pain. The SCS will be administered by asking the participant: "If 0 represents the most uncomfortable socket fit you can imagine and 10 represents the most comfortable socket fit, how would you score the comfort of the socket fit of your artificial limb at the moment?". The NIH developed a system of reliable, precise measures to be used to capture patient-reported physical, mental, and social well-being. The PROMIS tools are aimed at helping clinical researchers most appropriately quantify how a patient is feeling or what they are able to do.

- B. Comprehensive High-level Activity Mobility Predictor (CHAMP) Test: The CHAMP test will be used to assess overall amputee performance and the effect of the socket suspension intervention over time. The conglomeration of clinical assessment tools into the CHAMP was specifically done to measure high-level mobility in service members with a lower limb amputation. CHAMP consists of the Single Leg Stance Test (SLS), the Edgren Side Step Test (ESST), Illinois Agility Test (IAT), and T Test. The SLS measures the time an amputee is able to stand in single support with their hands on their hips and is performed with eyes open and with eyes closed. The ESST measures the ability of the participant to side shuffle back and forth in the layout shown in Figure 20 for 10 seconds. A point is given for each cone passed which is totaled for the 10 seconds. The IAT and T-test requires additional agility and control to navigate the course. Participants will complete the tasks in the following order: SLS, ESST, T-Test, and IAT. To generate a composite CHAMP score, the best times or point for each task is converted to a 0-10 scale following the scoring system. The

composite CHAMP score will range from 0-40, with 40 representing the highest level of performance.

- C. Biomechanical evaluation of gait: IU Neuroscience Gait lab will be used to collect kinematic data. The laboratory is equipped with an instrumented treadmill and infrared camera system. A harness system will be used to provide support and safety for the amputees while study participants walk on the treadmill for 6 minutes. A specially designed reflective marker set, will track movement between the socket and residual limb and allow analysis of motion not detected by the vacuum system, to quantify and characterize soft-tissue specific pistonning across suspension platforms. Reflective passive markers will be placed on the amputee and prosthesis, including the socket. A virtual marker position will be created for the residual limb from the physical markers. A series of segment definitions will be based off the reflective marker positions. The 3-dimensional position and orientation of a segment will be tracked relative to the segment immediately proximal using transformation matrices.
- D. Transcutaneous Oxygen Measurement and skin temperature:
The PeriFlux System 5000 uses non-invasive probes that will measure the skin temperature and transcutaneous Oxygen Measurement. The probe head is affixed to the residual limb by an adhesive sticker.
- E. Hyperspectral Imaging for tissue oxygenation and perfusion:
Powered by spatial frequency domain imaging, this imaging system provides a more complete picture of tissue health by quantifying and mapping tissue oxygenation and perfusion. Data are displayed in the form of color-coded maps.

X. Potential Risks:

There may be risks that are not known about at this time. Side effects, risks, and discomforts may result from study participation.

Prosthesis placement: While the goal of this project is to create a more comfortable prosthesis, it is possible that the subject could experience discomforts commonly associated with prosthesis use, such as perspiration, dry skin, rash, itching, blisters, high pressure in the socket, looseness in the socket, and mechanical rubbing that leads to ulceration which may lead to infection and additional surgery. Subjects with low levels of arterial blood flow have an additional risk of ulceration.

Treadmill task:

There is a risk of falling during the research activities. This risk is mitigated by the ability of participants to self-select pace for the treadmill task and observation of treadmill activities by research staff.

Transcutaneous Oxygen Measurement and skin temperature:

The PeriFlux System 5000 poses minimal risk to the subject. Removal of the sticker after data acquisition may cause minor discomfort similar to removing a small band-aid.

Hyperspectral Imaging for tissue oxygenation and perfusion:

This non-invasive non-contact imaging technique poses minimal risk to the subject.

Ultrasound:

Ultrasound imaging is a noninvasive technique and is a minimal risk procedure.

TEWL and Surface Electrical Capacitance Measurements:

TEWL and Surface Electrical Capacitance measurements are noninvasive and propose less than minimal risk.

Loss of Confidentiality

Although efforts are made to protect your study records, there is always a risk that someone could get access to your private health records.

XI. Unanticipated Problems and Adverse Event Reporting

Protocol deviations and Unanticipated Problems Involving Risks to Subjects or Others, Adverse Events, and Other Problems will be reported to the Indiana University per IU IRB reporting requirements.

Unanticipated problems can occur in any type of research (medical or non-medical) and may include occurrences such as adverse events, subject complaints, protocol deviations, and other untoward events involving risk. Events requiring prompt reporting by investigators and research staff may involve physical, psychological, social, legal, or economic harms.

Event reports and accompanying information will be screened for completeness by research staff members, additional clarifications will be requested from the investigator as necessary. Research staff members and the principal investigator will make an initial determination about whether the event represents a possible unanticipated problem involving risks to subjects or others and/or potential noncompliance. Reports of events determined during screening to represent possible unanticipated problems involving risks to subjects or others and/or serious/continuing noncompliance will be forwarded to the IRB for convened review. Reports of events that do not meet the requirements for prompt reporting may be reported at time of study renewal.

XII. Discontinuation Criteria

Patients will be informed during the informed consent process (in writing and verbally) that they are free to withdraw from the trial at any time. The Investigator may exercise his medical judgment to terminate a patient's participation in the trial due to clinically relevant changes in any clinical or laboratory parameter. The Sponsor-Investigator also reserves the right to discontinue/terminate the trial at any time.

Discontinuation criteria for individual subjects include: (1) Non-compliance with the inclusion/exclusion criteria, (2) treatment non-compliance, such as use of another socket, (3) withdrawal from the study due to reasons not related to the treatment.

XIII. Procedures for Amendment of Protocol:

Protocol modifications will be approved by the IU IRB prior to implementation and WRNMMC site HQ will be notified if the change is significant or adversely impacts the risk/benefit assessment for the study.

As per IU HRPP guidance on NSR devices reviews trial monitoring, an internal review of data/source verification will be performed and documented on a quarterly basis. The internal reviewer will conduct the following activities: quarterly observation of research recruitment, informed consent process, research activities completed at research study visits, data collection and analysis. The internal review process may meet more frequently as deemed necessary and will be immediately notified of any serious and/or unanticipated event(s) related to procedures of the study. They will review all summary data, overall progress of the study and any individual serious and/or unanticipated event report(s). They do not have any conflicts of interest with the study team and/or protocol. In addition, a Data Safety Monitoring Board (DSMB) will provide independent oversight of the study, and will meet with the PI and research team at the following intervals: (1) prior to enrollment, after enrollment of the first 15 subjects for Aim 2, after enrollment of the first 30 subjects for Aim 3, and after all subjects have been enrolled and within 60 days of completion of the study for both Aims 2 and 3. The DSMB will consist of a physician chairperson, a statistician, and a clinical trialist/ethicist. The Data Safety Monitoring Board will meet at the same intervals separate of the internal research reviewer. .

XIV. Payment:

All subjects will be compensated \$100 for each of the completed visits. Aim 1 subjects will be compensated \$100 for the completed study visit 1. Aim 2 subjects will have 4 total visits and will be eligible for a maximum of \$400 for completion of all study visits. Aim 3 subjects will have 3 total visits and will be eligible for a maximum of \$450 for the completion of all visits per following schedule: Visit #1 (\$50), Visit #2A & B (\$150, for completing all socket fitting activities

& baseline) and Visit #3A&B (\$250). Subjects will not be paid if any of study visits are not completed.

XV. Statistical Analysis:

Patient demographics and clinical characteristics will be described using frequencies and percentages for categorical data and median and the interquartile range (IQR) for continuous data. In Aim 1, random-effects linear regression will be used to assess the relationship between wave amplitude and distal movement (or lateral shift) controlling for vacuum pressure. Patient ID will be the random-term in the model. In Aim 2, random-effects linear regression will also be used to compare percent change in limb perfusion across adaptive EVS and suction at 12 weeks controlling vacuum pressure and controlling for the baseline EVS and suction values. In Aim 3, a random-effects linear regression model will be used to establish the relationship in amputee performance (as measured by the CHAMP tasks) and residual limb health across EVS and suction and across EVS and pin-locking/lanyard in a cross-over design. The model includes terms for group (EVS vs. suction or EVS vs. pin-locking/lanyard), sequence (EVS to suction vs. suction to EVS or EVS to pin-locking/lanyard vs. pin-locking/lanyard to EVS), and visit (second vs. first). All statistical models will account for the effect of age, diabetes status and smoking history by including them as the covariates in the models. As per need, subjects may be stratified based upon diabetes status and arterial blood flow status. The *p*-values produced in the study will be adjusted using the Holms procedure to control the overall type I error at 0.05 due to the multiple comparisons. All analyses will be run using Stata 13.1, Stata Corporation, College Station, Texas.

XVI. References:

1. Lake, C. The evolution of upper limb prosthetic socket design. *Journal of Prosthetics and Orthotics* 20, 85 (2008).
